### **8.1.3. Inclusion/Exclusion Criteria**

All inclusion (Section 5.1) and exclusion (Section 5.2) criteria must be reviewed by the Investigator or qualified designee to ensure the patient qualifies for study participation.

Both the Investigator and Alexion must approve patient eligibility before enrollment.

### **8.1.4. Study Drug Administration**

This section describes the dosage regimen of study drugs. At the scheduled dosing visits (Section 1.3), study drug infusion should be performed after all other tests and procedures have been completed, excluding the postdose blood sampling for PK and free C5.

Refer to Section 6 for additional information on study drugs including preparation, handling, storage, and accountability. For detailed instructions, refer to the Pharmacy Manual.

The ravulizumab dose for each patient will be based on last recorded body weight. The dosing regimen (Table 6) consists of a loading dose followed by maintenance dosing administered q8w. The maintenance dose should be initiated 2 weeks after the loading dose administration.

**Table 6: Weight-based Doses of Ravulizumab**

	Body Weight (kg)a, b	Dose (mg)
Loading dose	≥ 40 to < 60	2400
	≥ 60 to < 100	2700
	≥ 100	3000
Maintenance dose	≥ 40 to < 60	3000
	≥ 60 to < 100	3300
	≥ 100	3600

a Dose regimen will be based on the last recorded study visit body weight.

b In the event that a patient drops below 40 kg during the course of the study the approved ravulizumab aHUS dosing for patients weighing 30 - 40 kg will be used: a loading dose of 1200 mg and maintenance dose of 2700 mg, and in the event that a patient drops below 30 kg during the course of the study the approved ravulizumab aHUS dosing for patients weighing 20 - 30 kg will be used: a loading dose of 900 mg and maintenance dose of 2100 mg.

Abbreviation: aHUS = atypical hemolytic uremic syndrome

For each patient, the entire treatment duration is up to 156 weeks, consisting of a Randomized Controlled Period (50 weeks) and an Open-Label Extension Period (up to 106 weeks). Study drug administration will end when all patients have completed the 2-year Open-Label Extension Period, or ravulizumab is approved and/or available (in accordance with country-specific regulations), or anytime during the Open-Label Extension Period at the discretion of Alexion, whichever occurs first.

#### **8.1.4.1. Randomized Controlled Period**

The Randomized Controlled Period is a double-blind, randomized, placebo-controlled period. Eligible patients will be randomized 2:1 to receive blinded doses of ravulizumab or placebo during the Randomized Controlled Period (Day 1 through Week 42).

- Patients in the ravulizumab group will receive a blinded loading dose of ravulizumab on Day 1, followed by a blinded maintenance dose on at Week 2 (Table 6), then once q8w up to Week 42 (inclusive) (Table 6).
- Patients in the placebo group will receive a blinded matching placebo dose via IV infusion on Day 1, followed by a blinded matching placebo maintenance dose at Week 2, then q8w up to Week 42 (inclusive).

#### **8.1.4.2. Open-Label Extension Period**

Patients who elect to continue treatment after completion of the Randomized Controlled Period enter the Open-Label Extension Period at the completion of all scheduled predose assessments for the Week 50 visit and before receiving ravulizumab.

- Patients in the placebo group may switch to receive a blinded loading dose of ravulizumab at Week 50 (Table 6).
- To ensure treatment allocation remains blinded to patients, Investigators, and site staff, as well as Sponsor staff or delegates, patients in the ravulizumab group will receive a blinded ravulizumab dose of 900 mg at Week 50. The 900 mg dose at Week

50 is chosen to ensure maintenance of complete C5 inhibition until the next scheduled maintenance dose.

Starting at Week 52, all patients will receive open-label ravulizumab maintenance doses q8w (Table 6) until the end of the Open-Label Extension Period when all patients have completed 2 years of ravulizumab or ravulizumab is approved and/or available (in accordance with country-specific regulations). Patients may be allowed to switch from the 10 mg/mL to the 100 mg/mL formulation of ravulizumab with no change to the weight-based dose regimen at or after Week 52 in the OLE Period.

### **8.1.5. Visits at Home or Alternative Healthcare Facilities**

If available, patients may have an opportunity to receive study drug administration remotely at a medical facility that is located near the patient's home or at the patient's home with the permission of the Investigator, after discussion with the Alexion medical monitor (or delegate), in accordance with all national, state, and local laws or regulations of the pertinent regulatory authorities. Home infusions may be considered only for patients who have tolerated previous drug infusions well, without clinically significant infusion reactions, at the study site.

Remote visit options may be at the Investigator's discretion and oversight, in accordance with the local regulations, and conducted by a qualified medical professional. Information about AEs, concomitant medications, and ALS signs or symptomatology must be sent to the Investigator's site for evaluation on the day of the remote visit. In case of any signs or symptoms indicating an SAE, the patient may need to be evaluated at the study site or in an emergency room setting.

Monitoring, treatment, and management of infusion reactions for patients receiving drug infusions at home are described in Section 10.13.

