**Table 2: Schedule of Activities: Week 50 to Week 116**

Period	Open-Label Extension Period										Notes
Visit a		14	15	16	17	18	19	20	21	22	Additional visits can be performed as needed. An ED Visit should be performed if patients discontinue early (Table 3).
Week	W50	W52	W60	W68	W76	W84	W92	W100	W108	W116	
Days and Window	D351 ± 3	D365 ± 3	D421 ± 7	D477 ± 7	D533 ± 7	D589 ± 7	D645 ± 7	D701 ± 7	D757 ± 7	D813 ± 7	
Biomarker Research											
Blood samples for biomarker			T			T			T		
Blood samples for DNA and RNA									T		Optional; samples collected from patients who consent to DNA and RNA collection. The blood sample for RNA is collected at all time points and the blood sample for DNA is collected on Day 1. f
Urine samples for biomarkers			X			X			X		
Administration of Study Drug											
Ravulizumab h	X g	X	X	X	X	X	X	X	X	X	Administer after all other required tests/procedures.

Note: P = postdose; T = trough (predose); X = anytime.

Abbreviations: ADA = antidrug antibody; AE = adverse event; ALSFRS-R = revised amyotrophic lateral sclerosis functional rating scale; C5 = complement component 5; C-SSRS = Columbia-suicide severity rating scale; D = day; ECG = electrocardiogram; ED = early discontinuation; EQ-5D-5L = European Quality of Life Health 5-item questionnaire; HHD = handheld dynamometry; PK = pharmacokinetics; SVC = slow vital capacity; W = week; WOCBP = women of childbearing potential

a Under reasonable occasional circumstances where a patient is not able to attend a study visit on site, a home visit (where available) or visit at an alternative healthcare facility may be permitted by the Sponsor after discussing with the Alexion Medical Monitor (or delegate). This will be a case-by-case decision (Section 8.1.5).

b Ravulizumab dosing is based on the last recorded study visit body weight. When possible, weights should be obtained at every dosing visit; consecutive weights must not be more than 16 weeks apart.

c Performed by the Investigator or any designee who has been properly trained and certified for the evaluation, preferably the same Investigator or designee, throughout the study. When possible, ALSFRS-R should be performed first, SVC second, and HHD should be performed as last assessment prior to dosing.

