## **6. STUDY DRUG**

Study drug is defined as any investigational drug(s), marketed product(s), placebo, or medical device(s) intended to be administered to a study participant according to the study protocol.

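### The tolerance condition for home infusion can be met on placebo alone, so a placebo-arm patient's first ravulizumab dose, at Week 50, could be approved for home

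*Protocol*

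**What the plan says.** Protocol Section 8.1.5 lets study drug be given at a nearby medical facility or at home, with the Investigator's permission after discussion with the medical monitor. It adds a condition for the home only: "Home infusions may be considered only for patients who have tolerated previous drug infusions well, without clinically significant infusion reactions, at the study site". The term for the earlier infusions is not defined there. Section 6 counts placebo as study drug: "Study drug is defined as any investigational drug(s), marketed product(s), placebo, or medical device(s) intended to be administered".

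Under Section 8.1.4.1, placebo patients receive placebo on Day 1, at Week 2, and every 8 weeks to Week 42. Section 8.1.4.2 then says: "Patients in the placebo group may switch to receive a blinded loading dose of ravulizumab at Week 50". At the same visit the ravulizumab arm gets a blinded 900 mg dose. The reason given is "To ensure treatment allocation remains blinded to patients, Investigators, and site staff, as well as Sponsor staff or delegates".

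Footnote a of the schedule of activities (Tables 1 to 3) applies to the whole visit row. When a patient occasionally cannot attend, "a home visit (where available) or visit at an alternative healthcare facility may be permitted by the Sponsor", decided case by case. It names no excluded visit.

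**The concern.** The purpose of the condition is to see that a patient tolerates the infusion under site supervision before dosing moves to the home. Table 4 of the protocol lists systemic infusion-associated reactions as a potential risk, and Appendix 13 (Section 10.13) includes breathing difficulty among the signs. In the placebo arm at Week 50 the condition shows only that placebo was tolerated. A patient with no antibody exposure could therefore satisfy a rule meant to establish tolerance, and receive the first antibody infusion, a full loading dose, at home.

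**Working it through.** The plan states no figure to reproduce. The check is mainly a comparison of texts.

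**1. Infusions before Week 50** (Table 1; Section 8.1.4.1). Day 1 and Weeks 2, 10, 18, 26, 34 and 42 make 7. In the placebo arm, 0 of the 7 contain ravulizumab. In the ravulizumab arm all 7 do, and the first cannot be at home because no earlier infusion exists.

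**2. Which infusions count** (Sections 8.1.5 and 6). If placebo counts, as the Section 6 definition suggests, the condition can be met without antibody exposure. If only ravulizumab counts, it cannot be applied patient by patient at Week 50, because Section 8.1.4.2 keeps Investigators, site staff and Sponsor staff or delegates blinded then. Approvers could comply only by refusing home dosing to everyone at that visit, and nothing written tells them to.

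**3. Is Week 50 excluded elsewhere?** Footnote a of Table 1 (which contains the Week 50 visit) and of Table 2 (which contains the Week 50 dosing column) excludes no visit. Section 8.1.5 refers to Section 10.13 for reactions at home. That appendix gives general reaction management, anaphylaxis criteria and Sponsor notification, with no rule on home dosing, first active dose or Week 50.

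**4. Week 52.**

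| Week 50 infusion | Week 52 in the placebo arm is |
|---|---|
| Given at the study site | second ravulizumab infusion, after one tolerance check on site |
| Given at home or at a nearby facility | second ravulizumab infusion; all earlier on-site infusions were placebo |
| Missed | first ravulizumab infusion |

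**5. Ceiling on patients** (Section 9.2: 354 patients, 2:1, 20% dropout, about 82% one-year placebo survival).
- Planned placebo patients: 354 / 3 = 118.
- Reaching Week 50 if the 20% already includes deaths: 118 × 0.80 = 94.4, about 94.
- Reaching Week 50 if mortality is separate: 118 × 0.80 × 0.82 = 77.4, about 77.

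These count placebo patients who could reach Week 50, not home infusions. Entry to the extension is elective, and home uptake is not given.

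**The case against.** The strongest reply is that a home infusion at Week 50 is hard to arrange and already subject to judgment. Entry to the extension comes "at the completion of all scheduled predose assessments for the Week 50 visit and before receiving ravulizumab". Those assessments include dynamometry, vital capacity, ECG, physical and neurologic examination, laboratory tests and timed predose samples. Dynamometry has no stated home provision, and home-only vital capacity is accepted only when the pandemic prevents a clinic measurement. Section 8 requires adherence to the schedule and allows no waivers. A home visit also needs Investigator permission, medical monitor discussion and Sponsor permission. A qualified professional conducts it, information reaches the site the same day, and if a serious event is suspected, "the patient may need to be evaluated at the study site or in an emergency room setting". Approvers know that every Week 50 infusion is ravulizumab and can refuse all home requests without knowing the arm.

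All of this stands, and it makes the event unlikely. It does not supply the missing rule: footnote a can still permit a home visit at Week 50, and the remaining controls are discretionary.

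Three stronger readings are tempting, and the documents support none of them.
- A reader might infer that Week 52 has the same problem whenever Week 50 was given off site. In that case Week 52 is the second ravulizumab infusion; it is the first only if Week 50 was missed.
- A reader might take 118, or 77 to 94, as the number at risk. They are ceilings on eligibility.
- A reader might see extra hazard in the placebo arm's Week 50 dose of 2400 to 3000 mg (40 kg or more), which is 2.7 to 3.3 times the other arm's 900 mg. The documents give no relation between dose and reactions, so the ratio says nothing about hazard.

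**Conclusion.** The gap is real but small. As worded, the Section 8.1.5 condition can be met on placebo infusions alone, and no available text stops blinded approvers from allowing a placebo patient's first ravulizumab infusion at home at Week 50. The probability is low and the number affected cannot be estimated, so this is a minor safety improvement. The documents do not show that any such infusion was planned or took place.

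The conclusion assumes that the Pharmacy Manual, which was not available, does not already restrict home dosing at Week 50. A note to file says that Amendment 6 was never implemented. Its change table lists no change to Section 8.1.5, however, and the amendment history attributes the global home-visit allowance to Amendment 5. The SAP version history records that the study met its futility criterion, so the practical value now lies in any continued or reused version of this text.

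**What to change.** State in Section 8.1.5 and in footnote a of Tables 1 and 2:
- A patient's first infusion in the open-label extension (normally Week 50, or the next infusion given if Week 50 is missed) must not be given at home in either arm. It is given at the study site or, if travel there is impossible, at a medical facility.
- Home infusion afterwards requires that this first extension infusion was tolerated, at the site or that facility, without a clinically significant reaction.

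Weeks 2 to 42 stay unchanged. The rule is identical in both arms, so it does not reveal prior allocation. Counting a tolerated infusion at a medical facility matters: a rule that accepted only the study site could bar patients who cannot travel from home dosing for the whole extension.

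The cost is one or two sentences, plus the loss of the home option for that one infusion. Ravulizumab-arm patients, already exposed to the drug, bear that loss too, because a rule that spared them would reveal the arm.

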## **8.2. Efficacy Assessments**

### **8.2.1. Amyotrophic Lateral Sclerosis Functional Rating Scale-Revised (ALSFRS-R)**

The ALSFRS-R (Cedarbaum, 1999) is a validated instrument for evaluating the levels of the functional status of patients with ALS in 4 areas, including bulbar, gross motor activity, fine motor activity, and respiratory functions. The scale includes 12 functional items and each item is rated on a 0 to 4 scale, with a maximum total score of 48 (Section 10.6). A higher score indicates greater retention of function.

In this study, the ALSFRS-R will be performed throughout the study by the Investigator or any designee who has been properly trained for the evaluation. When possible, it is highly recommended that all assessments be performed by the same assessor.

The ALSFRS-R will be assessed as indicated in the SoA (Section 1.3). At the time points specified in the SoA, or if a patient is not able to attend the scheduled onsite visit, the ALSFRS-R can be assessed via a phone call by the Investigator or trained designee.

### **8.2.2. Ventilation Assistance-Free Survival (VAFS)**

Ventilation Assistance-Free Survival is a composite endpoint of survival and severe and irreversible respiratory decline. The use of VAFS allows for the collection of survival data that is not impacted by survival prolongation from noninvasive or permanent ventilatory interventions

which can prolong life without impacting underlying disease progression. The composite endpoint of VAFS (Paganoni, 2014) that will be used as a secondary endpoint for this study will be defined as the first occurrence of:

- All-cause mortality
- First use of NIV for  $\geq 22$  hours per day for  $\geq 10$  consecutive days
- First use of PAV for  $\geq 22$  hours per day for  $\geq 7$  consecutive days

Information on the components of VAFS will be assessed at every dosing visit by the Investigator or designee (see Section 1.3) using the ventilator assistance utilization form. An attempt will be made to obtain information about survival at the Follow-up phone call.

### **8.2.3. Slow Vital Capacity (SVC)**

Slow vital capacity is a spirometry technique that utilizes slow and gradual expulsion of air from the lungs. The full volume of expired air is measured as a proportion of the expected vital capacity of the patient based on biometric features such as age, height, and sex.

Slow vital capacity evaluation will be performed in the clinic by the Investigator, or any designee who has been properly trained for the evaluation, at screening and time points specified in the SoA (Section 1.3). When possible, it is highly recommended that all assessments be performed by the same assessor. In addition to SVC in the clinic, home SVC (where regionally available) should be performed using a provided spirometer and under the direction of study staff properly trained for the evaluation. In the event that an SVC measurement cannot be obtained in the clinic due to the COVID-19 pandemic, only home evaluation is required for that visit. Home SVC at screening should be performed after informed consent and after the patient has received training on the spirometer. For subsequent visits, including Day 1, home SVC should be performed within 3 days prior to the scheduled clinic visit.

### **8.2.4. Handheld Dynamometry (HHD)**

Handheld dynamometry (HHD) (Shefner, 2016) is a procedure for quantitative strength testing. This testing will be conducted by the Investigator or any designee who has been properly trained for the quantitative muscle strength evaluation. When possible, it is highly recommended that all assessments be performed by the same assessor. Muscle strength testing will be performed on prespecified muscles in the upper and lower extremities bilaterally and the force measurements recorded. Handheld dynamometry will be assessed at the time points specified in the SoA (Section 1.3).

### **8.2.5. Amyotrophic Lateral Sclerosis Assessment Questionnaire (ALSAQ-40)**

The ALSAQ-40 is a validated ALS-specific instrument for measuring quality of life in patients with ALS. There are 40 items covering 5 discrete categories (physical mobility, activities of daily living and independence, eating and drinking, communication, and emotional reactions) (Section 10.7). Patients will be asked about the difficulties they have experienced in the past 2 weeks and the frequency of each event by selecting 1 of the 5 available options. The ALSAQ-40 will be self-assessed by patients.

### **8.2.6. EuroQoL 5 Dimensions (EQ-5D-5L)**

The European Quality of Life (EQ-5D-5L) (Section 10.8) is a self-assessed, standardized instrument to measure health-related quality of life and has been used in a wide range of health conditions, including ALS (Schrag, 2000). The EQ-5D-5L consists of 2 pages: the EQ-5D-5L descriptive system and the EQ visual analogue scale (EQ VAS). At time points specified in the SoA (Section 1.3), or if a patient is not able to attend the scheduled onsite visit, EQ-5D-5L can be assessed via a phone call.

#### **8.2.6.1. EQ-5D-5L Descriptive System**

The descriptive system is a 5-component scale including mobility, self-care, usual activities, pain/discomfort, and anxiety/depression (Section 10.8). Each level is rated on a scale that describes the degree of problems in that area.

#### **8.2.6.2. EQ Visual Analogue Scale**

The EQ-5D-5L VAS is an overall health state scale where the patient selects a number between 0 and 100 to describe the condition of their health, with 100 being ‘The best health state you can imagine’ and 0 being ‘The worst health state you can imagine’ (Section 10.8).

This information can be used as a quantitative measure of health outcome as judged by the individual respondents. Previously published studies by EuroQol Group members showed preliminary evidence of the instrument’s feasibility, reliability, and validity.

### **8.2.7. Short Form Health Survey (SF-36)**

The SF-36 (Section 10.8.2) is a 36-item self-report of health-related quality of life (Stewart, 1988; Ware, 1992). It contains 8 subscales measuring different domains of health-related quality of life: physical functioning, role limitations due to physical problems, bodily pain, general health perceptions, vitality, social functioning, role limitations due to emotional problems, and mental health. The SF-36 will be conducted at screening and at timepoints specified per SoA (Section 1.3) The 2 summary scores are the physical component summary and the mental component summary. There is no single overall score for the SF-36.

### **8.2.8. Treatment Satisfaction Questionnaire for Medication (TSQM)**

The Treatment Satisfaction Questionnaire for Medication (TSQM-9) assesses 3 key dimensions of treatment satisfaction: Effectiveness (3 items); Convenience (3 items); and Global Satisfaction (3 items) (Bharmal, 2009). The instrument has been validated in chronic diseases including ALS (Meyer, 2019). The recall period for the TSQM is the previous 2 to 3 weeks or since last use. The TSQM-9 can be used to estimate total TSQM score, score for effectiveness, and score for convenience. The TSQM-9 will be administered at Day 1 and at timepoints specified in the SoA (Section 1.3).

## **8.3. Safety Assessments**

The planned schedule for all safety assessments is provided in the SoA (Section 1.3).

### **8.3.1. Physical Examinations**

- A complete physical examination will include, at a minimum, assessments of the following organs/body systems: skin, head, ears, eyes, nose, throat, neck, lymph nodes, chest, heart, abdomen, extremities, and musculoskeletal.
- An abbreviated physical examination will include, at a minimum, a body-system relevant examination based upon Investigator judgment and patient symptoms.
- Examiners should pay special attention to clinical signs related to previous serious illnesses.
- For consistency, all efforts should be made to have the physical examination performed by the same qualified study staff at each study visit.
- Additional physical examinations can be performed as medically indicated during the study at the Investigator's discretion.

